7 MEASUREMENTS OF TREATMENT COMPLIANCE

Study participants will be provided with CZP outside the study; hence compliance will not be measured.

8 EFFICACY ANALYSES

Not applicable.

9 PHARMACOKINETIC AND IMMUNOGENICITY ANALYSES

9.1 Statistical analysis of the primary outcome variable

9.1.1 Derivations of primary outcome variable

The primary endpoint will be summarized and listed using the PK-PPS. Individual samples marked 'Excluded from analysis' according to the PD review log 'Action for analysis' column will be deselected from the primary analysis.

Predose and postdose plasma CZP concentrations in women during pregnancy, relative to postpartum, will be analyzed as measured. Data analysis may be conducted on log transformed data (and back-transformed results displayed) where necessary.

9.1.2 Primary analysis of the primary outcome variable

The CZP plasma concentrations (primary variable) will be analyzed using a linear mixed effects model with fixed effects for disease phenotype, gestational week, trimester [trimester 1, 2, 3, or postpartum] and whether the sample was predose or postdose [binary indicator], and the random effect will be study participant. Within this model trimesters will be defined as follows: trimester 1 (≤ 12 weeks and 6 days' gestation), trimester 2 (13–28 weeks and 6 days' gestation), trimester 3 (≥ 29 weeks' gestation) and postpartum.

A compound symmetry covariance structure will be used, as this was decided to be the most appropriate structure given the context of this data. In case of overfitting, disease phenotype will be excluded from the model.

Adjusted mean differences with 95% CI of CZP plasma concentrations between samples taken each pregnancy trimester and postpartum will be estimated within this linear mixed effects model using contrasts. These adjusted mean differences and 95% CIs will be displayed graphically in a forest plot.

ICC may be provided to describe the consistency of CZP absorption from the same participant based on the linear mixed effects model as described in Section 3.1.1.

Data analyses may be conducted on log-transformed data, based on visual inspection of the data. This will be based on visual inspection of histograms, boxplots and quantile-quantile plots for each dosing regimen which will be included as part of the statistical appendices. If the data show a departure from normality, data analysis will be conducted on log transformed data (and back-transformed results displayed).

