1.3 Schedule of Activities

The Schedule of Activities is provided in [Table 1–1](#).

This document cannot be used to support any marketing authorization application and any extensions or variations thereof.
PUBLIC COPY

Table 1-1: Schedule of Activities

Procedure ^a	Screening	Sampling Period					SFU/EWD (via telephone) ^c
		Pregnancy Period			Postpartum Period ^b		
		V1 ^d	V2 (Enrollment)	Predose ^e (Q4W)	Postdose ^f (Q8W)	V5 Predose ^e	V6 Postdose ^f (optional)
Informed consent	X						
Demographics and baseline characteristics ^h	X						
Verification of inclusion/exclusion criteria	X	X					
Significant medical/procedures history and concomitant diseases	X						
Concomitant medication and procedures review	X	X	X	X	X	X	X
Adverse event review ⁱ	X	X	X	X	X	X	X
Recording of commercial CZP treatment ^j	X	X	X	X	X	X	X
Physical examination ^k	X						
Vital signs ^l	X						
Tobacco and alcohol consumption, and drug abuse	X						
TB questionnaire ^m	X						

Table 1-1: Schedule of Activities

Procedure ^a	Screening	Sampling Period					SFU/EWD (via telephone) ^c
		Pregnancy Period			Postpartum Period ^b		
		V1 ^d	V2 (Enrollment)	Predose ^e (Q4W)	Postdose ^f (Q8W)	V5 Predose ^e	V6 Postdose ^f (optional)
TB test (if not within 6 months) ^{n,o}	X						
Blood sampling for plasma CZP PK levels		X	X	X	X	X	
Blood sampling for plasma anti-CZP antibodies		X	X			X	
Study participant diary completion/review	X	X	X	X	X	X	
Blood sampling for CRP and albumin		X	X			X	
Weight (for BMI calculation)		X	X			X	
Pregnancy outcome						X	
SFU contact							X

BCG=Bacillus Calmette–Guérin; BMI=body mass index; CRP=c-reactive protein; CZP=certolizumab pegol; EWD=Early Withdrawal/Discontinuation; ICF=informed consent form; PK=pharmacokinetic; Q4W=every 4 weeks; Q8W=every 8 weeks; SFU=Safety Follow-up; TB=tuberculosis; V=Visit

^a It is expected that PK samples may not be obtainable in every case. Therefore, missing samples should not be considered major protocol deviations.

^b Postpartum samples will be collected up to 13 weeks (± 3 days) postpartum.

^c The SFU telephone contact will take place 5 weeks (± 5 days) after the last study visit for all study participants.

^d Visit 1 may take place at an on-site or off-site location, conducted by the investigator or appropriate designee (eg, study participant's local healthcare provider).

^e Predose samples will be collected within 4 hours prior to dosing.

Table 1-1: Schedule of Activities

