6.4 Treatment compliance

Study participants will be provided with a diary to record all CZP dosing dates and times over the study period.

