- “n” will be an integer.
- Mean, SD, and median will use 1 additional decimal place compared to the original raw value from the Case Report Form (CRF).
- Coefficient of variance (CV [%]) will be presented with 1 decimal place.
- Minimum and maximum will have the same number of decimal places as the original raw value.

If the number of decimal places reported in the raw data is varied then either the maximum raw number of reported decimal places or 3 will be used, whichever is the lowest, as a guide for the descriptive statistics.

Unless stated otherwise, statistical tests will be performed 2-sided and p-values will be rounded to 4 decimal places. P-values less than 0.0001 will be presented as “<0.0001” and p-values greater than 0.9999 will be presented as “>0.9999.” Statistical comparison will be performed at the 0.05 level of significance.

The SAS® outputs supportive of any statistical model (i.e., all excluding the descriptive analyses) will be provided as a separate PDF document in addition to TFLs. These outputs will be included in the ‘Documentation of Statistical Methods’ section of the clinical study report.

The abbreviation for certolizumab pegol is CZP and will be used in tables and listings headers. Unless otherwise specified, in the TFLs study participants on Certolizumab pegol will be displayed in columns by dosing regimen and all study participants as:

- “Not Dosed”
- “CZP 200mg Q2W”
- “CZP 400mg Q2W”
- “CZP 400mg Q4W”
- “All Dosed Participants”

An additional “Other” category will be added to the tables in case there are dosing regimens outside those listed. The “Not Dosed” category includes participants who enrolled but did not record a CZP dose relative to any PK samples prior to discontinuation. The “All Dosed Participants” category includes participants in CZP 200mg Q2W, CZP 400mg Q2W and CZP 400mg Q4W combined.

Study Participants will be grouped according to the commercial CZP dosing regimen that was in effect at enrollment (actual dose). Any participant with a dose reduction or increase will be summarized in the initial dosing regimen group.

All repeated and unscheduled measurements will be presented in the data listings, where applicable. The following general rules will apply to all repeated and unscheduled measurements:

- Unscheduled measurements will not be used in the descriptive statistics.
- For repeated measurements only the scheduled latest value can be used in the calculation of the descriptive statistics.

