4 STATISTICAL/ANALYTICAL ISSUES

4.1 Adjustments for covariates

The following covariates will be included in the primary analysis model specified in Section 9.1.2:

- disease phenotype
- gestational week
- trimester and
- dose point

The covariates will be defined as: disease phenotype (rheumatoid arthritis, psoriatic arthritis, psoriasis, Crohn's disease, axial spondyloarthritis and ankylosing spondylitis) a 6-category variable, gestational week (that is, at the time point when sample is collected) as a continuous variable, trimester (trimester 1, 2, 3, or postpartum) as a 4-category variable, and dose point (predose or postdose) as a binary variable. In case of overfitting, disease phenotype will be excluded from the model.

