9.1.4 Exploratory analysis of the primary outcome variable

The linear mixed effects model from the primary analysis will also be fitted to the predose and postdose CZP plasma concentrations separately. Adjusted means and 95% CI for each model will be included in the forest plot.

CZP plasma concentrations will additionally be analyzed adjusting for CRP, albumin and BMI. These analyses will be conducted using the same linear mixed effects model used for the primary analysis with CRP, albumin and BMI as a covariate in 3 separate models. Results from these models should be interpreted with caution, due to the small sample size and relatively large number of covariates. Summary tables showing the mean differences and 95% CIs of each trimester vs post-partum estimated from the model contrasts will be presented.

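### The primary PK model has no term for the dose or interval in force at sampling, so a regimen change within a woman would be read as a pregnancy effect

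*SAP*

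**What the plan says.** SAP 4.1 opens its list with "The following covariates will be included in the primary analysis model specified in Section 9.1.2" and names disease phenotype, gestational week, trimester and dose point, where dose point is only predose or postdose. SAP 9.1.2 repeats it: "with fixed effects for disease phenotype, gestational week, trimester [trimester 1, 2, 3, or postpartum] and whether the sample was predose or postdose". Participant is the sole random effect. SAP 9.1.1 takes concentrations as measured or log-transformed, without dose normalisation. The estimates of interest are contrasts of each trimester with postpartum.

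The variants in SAP 9.1.4 do not add dose. "The linear mixed effects model from the primary analysis will also be fitted to the predose and postdose CZP plasma concentrations separately", and CRP, albumin and BMI each enter one further model. Within SAP 9.1.2, regimen appears only in the plots that decide on log transformation, which include "quantile-quantile plots for each dosing regimen". In tables and figures, regimen means regimen at enrolment: "Any participant with a dose reduction or increase will be summarized in the initial dosing regimen group".

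Protocol 4.3 and 6.6 let the physician, or the woman herself, alter the regimen after entry, with a ceiling of 400 mg Q2W. Protocol 7.1.1 keeps women with modified or interrupted dosing under observation, including postpartum sampling. The data needed to describe dosing exist: "Study participants will be provided with a diary to record all CZP dosing dates and times over the study period". Protocol 9.3.1 also announces a population PK analysis that accounts for individual dosing. The SAP does not describe it.

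**The concern.** The study compares each woman's concentrations in pregnancy with her own postpartum reference. That comparison isolates physiology only if the dose and interval are the same on both sides. A participant intercept removes a regimen that never changes; it cannot remove one that changes between the samples being compared.

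The predose/postdose flag does not fill the gap. "Predose samples will be collected within 4 hours prior to dosing", so a predose sample lies about 14 days after the last dose on Q2W and about 28 days on Q4W. One flag value covers two different points on the concentration curve.

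The change need not be reversed by postpartum. If a woman changes in mid-pregnancy and stays on the new regimen, her earlier trimesters are the ones distorted. Protocol 2.2 wants these data to inform decisions about dose in pregnancy, so a dosing difference mistaken for physiology would affect the study's main use.

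**Working it through.** The plan states no figure for this bias and gives no SD, half-life or number of regimen changes. Everything below is illustrative.

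**Inputs.** From the documents: 15 evaluable women and a minimum of 10 with longitudinal data (Protocol 9.8); about 6 predose and 3 postdose pregnancy samples each; a postpartum predose sample and an optional postpartum postdose sample. Assumed: exposure proportional to dose; no true pregnancy effect; log-scale variances 0.25 between and 0.09 within women; half-life 14 days (the 70 days in Protocol 8.5 divided by 5), range 10–18.

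**1. Simple form.** If *k* of *n* women have dose ratio *f* between pregnancy and postpartum, the apparent geometric mean ratio is *f*^(*k*/*n*).

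| | k=2, n=15 | k=3, n=15 | k=2, n=10 |
|---|---|---|---|
| f = 2 | 1.097 | 1.149 | 1.149 |
| f = 0.5 | 0.912 | 0.871 | 0.871 |

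Doubling is possible only for women below the 400 mg Q2W ceiling. Opposite changes cancel in part: two women up and one down in 15 leave 2^(1/15) = 1.047.

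**2. Random-intercept model with trimester and dose point.** For 3 of 15 women doubling from trimester 2 and reverting, trimester 2 and 3 ratios are 1.107–1.187, depending on sampling layout and on which women have the optional postpartum sample. For halving they are 0.843–0.904. If 3 women double at week 20 and stay there postpartum, the ratios are 0.864, 0.943 and 0.996 for trimesters 1, 2 and 3.

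**3. With gestational week added, as the SAP plans.** For 3 of 15 women doubling, the trimester 3 ratio is still 1.156–1.161. Its SE rises from 0.077 to 0.103–0.269, depending on how week is coded postpartum, which the SAP does not state. As ln(1.16) is about 0.148, the bias falls from about 1.9 SE to about 0.6–1.4 SE. Two scenarios were simulated with week in the model, 2 of 10 women changing and 150 runs each. With the postpartum dose halved, ratios were 1.14–1.15 and 95% interval coverage 90–93%. With the dose doubled in trimesters 2 and 3, those ratios were 1.15–1.16 and coverage 95–99%.

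**4. Interval switch at equal dose rate.** Under a one-compartment model with r = 2^(−14/14) = 0.5, the trough is proportional to 200 × 0.5/0.5 = 200 on 200 mg Q2W and 400 × 0.25/0.75 = 133 on 400 mg Q4W, a ratio of 0.667. At day 7 the ratio is (400/0.75)/(200/0.5) = 1.333. If 3 of 15 women switch from Q2W to Q4W for pregnancy, the predose-only fit gives 0.667^(3/15) = 0.922; the pooled model gives about 0.96–0.97.

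**5. Which dose covariate works.** Dose received over the previous 28 days looks natural but fails in practice. A predose sample falls at the edge of that window, so a dose given a day late leaves a Q4W sample with no dose in it and a Q2W sample with half its true rate. In a simulation of 15 women with 3 doubling (week not in the model), dosing intervals varied by ±1 to ±3 days. With ±1 day, about 11% of predose samples had an undefined rate.

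| Dose term | Trimester 3 ratio | Dose coefficient |
|---|---|---|
| None | about 1.16 | – |
| 28-day window | 1.12–1.14 | 0.2–0.3 |
| Regimen in force | 1.01–1.03 | 0.91–0.95 |

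A second layout gave 1.13–1.15, 1.10–1.12 and 1.00–1.01.

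**6. Lag after a change.** Four weeks after doubling, with a 14-day half-life, exposure is 1 + (1 − 0.25) = 1.75 times the old level, not 2. A dose term that steps immediately leaves residual ratios of 0.961–1.035 over the half-lives and change times tried. An analysis limited to samples on the reference regimen and away from any change gives 1.000.

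**The case against.** The best defence is that the study is exploratory, tests no formal hypothesis, and requires at least 12 weeks of stable dosing and expected continuation at entry. Protocol 6.6 foresees dose changes and expects the planned methods to cope, and Protocol 9.3.1 assigns dosing variation to population PK, which still applies because SAP 1 defers to the protocol. Some of this stands: changes may be few, and population PK can use the affected data properly. But it is a separate analysis and leaves the primary contrast uncorrected. Exclusion through the deviation log may remove some samples, but its criteria are in a document not available here, and a permitted change is not on its face a deviation.

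Three stronger readings are not supported.

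- **That the primary estimate is biased.** The documents do not show that any woman changed regimen; with no changers the bias is zero.
- **That the confidence intervals break down.** Without gestational week, simulated coverage fell to 50–64% for 3 of 15 women with a halved postpartum dose. The SAP includes week, and the two scenarios run with it, both with 2 of 10 women, showed coverage of 90% or more.
- **That regimen changes will be concealed.** SAP 7 says "hence compliance will not be measured", but that concerns compliance with a product supplied outside the study. The enrolment-regimen grouping in SAP 3.1 affects displays and has no effect on the model.

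**Conclusion.** The omission is clear from SAP 4.1, 9.1.2 and 9.1.4, and the route to bias is direct whenever a woman's dose or interval differs between a pregnancy sample and her postpartum reference. Its size depends on numbers the documents do not give. Under dose proportionality, no true effect and same-direction two-fold changes that revert by postpartum, 3 of 15 women move the affected trimester ratios to about 1.15 or 0.87; mixed directions give less. In the model as planned, the harm is mainly to the point estimate, because gestational week widens the intervals. The remedy needs no new data, which makes this a cheap improvement worth making; it does not invalidate the design.

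**What to change.** 1. From the diary, derive for each PK sample the regimen in force (dose and interval) and the time since last dose. Add the log dose rate of the regimen in force as a time-varying covariate in SAP 9.1.2 and 9.1.4. Do not use a fixed 28-day trailing window. State a rule for samples taken during an interruption, for example leave them out of the model and list them.
2. Add a sensitivity analysis limited to samples on the same uninterrupted dose and interval as the woman's postpartum reference, outside a stated period after any change. This also covers switches such as 200 mg Q2W to 400 mg Q4W, which have equal dose rates and so escape the covariate.
3. Report by trimester the number of women and samples off the postpartum-reference regimen. Flag samples off the enrolment regimen in the SAP 9.1.3 displays, and cross-refer to the population PK analysis.

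The covariate costs one model degree of freedom. In the illustrative layouts, the SE of the trimester 2 and 3 contrasts rises by roughly 1–9% with 15 women and 6–13% with 10. The restricted analysis has an SE about 3–10% larger. Beyond that, the cost is SAP wording and some programming. Nothing here implies a change to clinical dosing.

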3.2.2 Study periods

The study consists of a Screening Period, Sampling Period (consisting of a Pregnancy Period and Postpartum Period), and a Safety Follow-up (SFU) contact, as described below. Gestational week (i.e., week of gestational age) is determined from the time since the first day of the last menstrual period or, if the participant had undergone in vitro fertilization (IVF), from the date of birth and gestational age recorded for the pregnancy outcome and then back-calculated to get the gestational week for each PK sample.

- Screening Period: Starts at the confirmation of pregnancy at screening and ends at the start of the enrolment date (Participant having taken CZP for at least 12 weeks at the same dosing regimen prior to the Enrollment Visit, which must take place at ≤ 10 weeks gestational age).
- Sampling Period: The total study duration for a study participant will be a maximum of 53 weeks (40 weeks gestation period and up to 13 weeks (± 3 days) postpartum).
 - Pregnancy Period: Starts at enrolment and ends on the day of delivery. Pregnancy may take the entire length of the gestation period (up to 40 weeks).
 - Postpartum Period: Starts the day after the date of delivery and ends after the final postpartum sample is taken.
 - Trimesters: Defined using the gestational week and distinguished as first (up to 12 weeks and 6 days’ gestation), second (13–28 weeks and 6 days’ gestation), and third (any time at or after 29 weeks’ gestation)
- Safety Follow-up contact: The SFU visit will be defined for all study participants who complete the study, or for study participants who discontinue early including those who discontinue from CZP. For participants who complete the study, the SFU will be conducted 5 weeks (± 5 days) after final study visit. For participants who discontinue, the SFU visit will still be completed.

In case that the SFU date is not available, the last contact date will be used as end of the SFU period. A participant is considered to have completed the study if she has completed all phases of the study per protocol including the final study contact (SFU).

The end of the study is defined as the date of the SFU/last contact of the last participant in the study.

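### The primary model adjusts the trimester/postpartum factor for the gestational week it is cut from, which makes the trimester-versus-postpartum contrasts imprecise, dependent on an unstated coding, and biased if concentrations trend within trimesters

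*SAP*

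**What the plan says.** SAP 9.1.2 specifies a linear mixed model with "fixed effects for disease phenotype, gestational week, trimester [trimester 1, 2, 3, or postpartum] and whether the sample was predose or postdose", a random participant effect and compound symmetry. SAP 4.1 enters "gestational week (that is, at the time point when sample is collected) as a continuous variable" and trimester as a 4-category variable that includes postpartum.

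Both variables come from the same clock. SAP 3.2.2 says "Gestational week (i.e., week of gestational age) is determined from the time since the first day of the last menstrual period"; for IVF pregnancies the week is "back-calculated to get the gestational week for each PK sample". The factor is cut from it: "Trimesters: Defined using the gestational week and distinguished as first", with boundaries at 13 and 29 weeks.

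The primary output is stated as "Adjusted mean differences with 95% CI of CZP plasma concentrations between samples taken each pregnancy trimester and postpartum will be estimated", and it goes into the forest plot. No contrast week is given, and no sentence says which week a postpartum sample carries. The only simplification rule is "In case of overfitting, disease phenotype will be excluded from the model". SAP 9.1.4 reuses the specification: "The linear mixed effects model from the primary analysis will also be fitted to the predose and postdose CZP plasma concentrations separately".

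**The concern.** A postpartum sample at 12 weeks after delivery sits at about week 51 from last menstrual period, well beyond any pregnancy sample. Holding gestational week constant while moving from a trimester to postpartum describes a state that cannot occur. The model can produce that comparison only by extrapolating one common slope, estimated from week-to-week variation inside the periods.

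Three consequences follow for the standard common-week contrast:

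- Precision is lost whatever the true profile.
- If concentrations change gradually within trimesters, which is the kind of change this study is meant to detect, the contrast no longer estimates the stated difference between samples in a trimester and samples postpartum.
- The result depends on the value a programmer gives postpartum samples. If that value is left missing, every postpartum row drops out and no contrast can be estimated.

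There is no formal hypothesis test, so these estimates and their 95% intervals are the main product of the primary analysis.

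**Working it through.** **Plan's own figure.** SAP 2.4 gives 15 evaluable participants (at least 10 with longitudinal data) with no SD, effect size or precision target, so there is no figure to reproduce.

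**Inputs from the documents.** Enrolment by week 10; predose samples Q4W and postdose samples Q8W, with about 6 + 3 expected; a 4 + 2 minimum for longitudinal data; postpartum predose sample at 12 (±1) weeks and an optional postdose sample a week later; compound symmetry.

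**Assumptions (not in the documents).** Delivery at about week 39; log scale; disease phenotype omitted; variance components and sample layouts as stated below. Results are exact generalised least squares.

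**Step 1: what the contrast is.** Let ȳ_k and w̄_k be the mean log concentration and mean week in period k, P denote postpartum, and b̂ the common slope. To a close approximation,

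- contrast_k = (ȳ_k − ȳ_P) + b̂ (w̄_P − w̄_k)
- variance ≈ SE₀² + (w̄_P − w̄_k)² SE(b̂)²

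where SE₀ is the standard error without week.

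**Step 2: precision.** Take 15 women on the full Q4W/Q8W schedule (about 12 pregnancy samples each), a postpartum pair, intraclass correlation 0.6, and the week count continued postpartum. Mean weeks are 9.5, 21.0, 33.5 and 51.1. SEs are in total-SD units.

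| | T1 | T2 | T3 |
|---|---|---|---|
| w̄_P − w̄_k | 41.6 | 30.1 | 17.6 |
| SE without week | 0.153 | 0.134 | 0.147 |
| SE as written | 0.585 | 0.429 | 0.281 |
| Ratio | 3.8 | 3.2 | 1.9 |

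Check against step 1: √(0.585² − 0.153²)/41.6, √(0.429² − 0.134²)/30.1 and √(0.281² − 0.147²)/17.6 are each about 0.0136. One extrapolated slope accounts for all of the inflation.

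SE ratios for other layouts (between/within SD 0.4/0.25, half the women with a postpartum postdose sample):

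| Layout | T1 | T2 | T3 |
|---|---|---|---|
| Strict Q4W/Q8W | 3.39 | 2.89 | 1.76 |
| 6 + 3, spread evenly | 4.25 | 3.57 | 2.12 |
| 6 + 3, random from the grid | 3.66 | 3.22 | 1.90 |
| 4 + 2 minimum | 4.06 | 3.74 | 2.10 |

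Over all layouts tried, the ranges are about 2.8–4.4, 2.5–3.7 and 1.6–2.1. The number of women (10 or 15) and the variance components hardly change them. In the 6 + 3 random layout, the T1 95% interval widens from ×/÷1.15 to ×/÷1.68. In the separate fits of SAP 9.1.4, the ratios are 3.1–3.4/2.8–3.1/1.7–1.8 for predose and 4.2–4.7/3.3–3.8/2.0–2.2 for postdose. The postdose ratios reach about 21/15/10 if all women's postdose samples fall at similar weeks.

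**Step 3: bias and coding.** Let log concentration fall 0.01 per week from week 0 and recover fully postpartum. True log differences are −0.01 × 9.5, 21.0 and 33.5, giving ratios of 0.91, 0.81 and 0.72.

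- Week continued: T1 = −0.095 − 0.01 × 41.6 = −0.511, T2 = −0.210 − 0.301 = −0.511, T3 = −0.335 − 0.176 = −0.511. The ratio is 0.60 in every trimester.
- Postpartum coded 40: T1 = −0.095 − 0.01 × 30.5 = −0.40, ratio 0.67, and the same in T2 and T3.
- Postpartum coded 0: T1 = −0.095 + 0.01 × 9.5 = 0, ratio 1.00, and the same in T2 and T3.
- Week omitted: 0.91/0.81/0.72.

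Other assumed profiles, week continued. The linear falls start near week 8 and reach the stated size by week 40.

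| Profile | True T1/T2/T3 | Reported |
|---|---|---|
| Linear, 10% fall | 0.99/0.96/0.92 | 0.87/0.87/0.87 |
| Linear, 25% fall | 0.98/0.89/0.79 | 0.68/0.68/0.68 |
| Linear, 40% fall | 0.96/0.81/0.66 | 0.51/0.51/0.50 |
| 25% fall, plateau at week 20 | 0.95/0.77/0.75 | 0.69/0.62/0.66 |
| U-shape | 0.97/0.81/0.85 | 0.74/0.66/0.76 |
| Flat or step | – | no bias |

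Starting the 25% linear fall at week 0 instead gives true ratios of 0.94/0.87/0.79, reported as 0.70.

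Coding also moves the SE ratios: about 2.9–3.3/2.2–2.4/1.2 with postpartum at 40, and 1.3–1.4/2.4–2.7/3.3–3.6 with postpartum at 0.

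**The case against.** - **The fault lies in the contrast, not the term.** If each period is evaluated at its own mean week, the SE ratio is 1.00 and the true ratios return with week still in the model. With no week-by-trimester interaction, the choice of a single common week changes nothing. Both points stand. But the SAP does not specify own-week contrasts, and the standard adjusted difference is the common-week one.
- **The text favours one coding.** SAP 3.2.2 and 4.1 tie week to each sample, and SAP 9.2.3 plots concentrations over the whole study by gestational week. That supports continuing the count postpartum. It stands as the best reading, although no sentence states it. It is also the coding with the largest distortion for T1 and T2.
- **The bias is hypothetical.** Protocol 2.3 reports that mothers in an earlier study had concentrations at delivery similar to those of nonpregnant women. That gives no support to a large fall, but a comparison at delivery cannot exclude a trend within pregnancy. The precision loss needs no trend.
- **The study is exploratory and has other summaries.** The trimester geometric means and plots in SAP 9.1.3 do not use week, and Protocol 9.3.1 plans a population PK analysis. These limit the risk of a wrong overall conclusion. They do not repair the primary estimate, and the SAP does not say which result prevails if they disagree.

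**Conclusion.** The concern holds and must be fixed. As written, and with the standard adjusted contrast, the primary analysis inflates standard errors about 3- to 4-fold for trimesters 1 and 2 and about 2-fold for trimester 3. With a within-trimester slope b per week, it shifts the contrasts by about +41b, +30b and +18b. A linear trend is then reported as one uniform ratio, and the gradient across trimesters is lost. Omitting week returns the true ratios to within 0.01.

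The sizes rest on assumed visit timing, delivery at about week 39 and the assumed concentration profiles. The mechanism does not, because trimester is cut from week and pregnancy and postpartum weeks cannot overlap. The overfitting rule removes only disease phenotype, so it does not help.

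**What to change.** Delete gestational week from the covariate list in SAP 4.1 and from the fixed effects in SAP 9.1.2, and so from the SAP 9.1.4 models. Keep the 4-level trimester/postpartum factor as the only time term.

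If a gestational trend is wanted, fit it in a separate pregnancy-only model. Alternatively, enter week centred within trimester and set to 0 postpartum; this was checked and returns the true ratios with an SE ratio of 1.00. If uncentred week is kept, state the value assigned to postpartum samples and evaluate each contrast at each period's own mean week.

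The cost is SAP wording and one fewer model term. No new data are needed. Protocol 9.3.1 makes these fixed effects optional, so no protocol amendment is required.
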